The goal of this project is to collect information in regards to the immunogenicity of PSA peptides in order to develop a novel therapeutic vaccine. This vaccine will consist of prostate specific antigen (PSA) peptide and Candida skin test reagent. Candida has recently been shown to be a promising new vaccine adjuvant for promoting T-cell responses (2). It can induce interleukin-12 (promotes T-cell response) secretion by Langerhans cells, the main antigen presenting cells in skin (3). In a Phase I clinical trial treating women with biopsy-proven high-grade squamous intraepithelial lesions (HSILs), precursors of cervical cancer, a combination of human papillomavirus peptides with Candida was demonstrated to be safe, to induce immune responses to human papillomavirus, and to promote T-helper type 1 (Th-1) response (promotes cell-mediated immunity) in vaccine recipients (4).

For treating prostate cancer, PSA is an ideal antigen as it is expressed in prostate cancer but not in any other organs. The characteristics of peptides that can effectively be used in therapeutic vaccines are their **solubility** in a single solution, **immunogenicity** in terms of containing large number of T-cell epitopes (so the vaccine can be used for all patients and not just a few that express certain HLA tissue types), and **ability to mature Langerhans cells** which in turn promotes T-cell activity.

In this protocol we focus on the immunogenicity of candidate peptides.

Specific Aims

To measure antigen-specific interferon- secretion by enzyme-linked immunospot (ELISPOT) assay, which measures antigen-specific interferon- secretion

Study Design and Procedures

Sixty ml of whole blood will be drawn in tubes containing sodium heparin from patients (n=10) diagnosed with prostate cancer. Blood will be drawn at the same time patients are having routine standard of care labs done. Up to 20 subjects could be screened in order to reach the enrollment goal of 10 subjects.

Five PSA peptides have been selected for (1) having neutral or positive charges and (2) containing <30% hydrophobic residues: PSA 1-40 (Ac-MWVPVVFLTLSVTWIGAAMPLSRIVGGWECEKHSQPW QV-NH2), PSA 41-80 (Ac-LVASRGRAVCGGVLVHPQWVLAAHCIRNKSILLGRHSL-NH2), PSA 161-200 (Ac-EPEEFLTPKKLQCVDLHVISNDVCAQVHPQKVTKFMLCAG-NH2), PSA 81-120 (Ac-FHPEDTQVFQVSHSPHP LYDMSLLKNRFLRPGDDSSH-NH2), PSA 201-240 (Ac-RWTGGKSTCSGDSGGPLVCNGVLQGITSWGSEPCA LPER P-NH2), PSA 241-261 (Ac-SLYTKVVHYRKWIKDTIVANP-NH2).

Peripheral blood mononuclear cells (PBMCs) will be purified using the ficoll gradient centrifugation method. 96-well plates (MultiScreen-HA; Millipore, Bedford, MA) will be coated with 5 μ g/ml of primary anti-interferon-gamma monoclonal antibody (Mabtech, Stockholm, Sweden) for capture in 50 μ l/well of phosphate-buffered saline (PBS) and stored at 4°C overnight. The plates will be washed four times with PBS and blocked using RPMI 1640 with 5% pooled human serum for 1h at 37°C. Three hundred thousand PBMC per well in triplicate will be presented with 10microM each of the PSA peptides described above.

Phytohemagglutinin will be used as a positive control while media containing no peptide will serve as a negative control. Human recombinant interleukin-2 (R&D Systems, Inc., Minneapolis, MN) (20U/ml) will be added to all wells. After 40 +/- 2h incubation at 37°C, the plate will be washed four times with PBS containing 0.05% Tween-20. A total of 50microl of secondary antibody (biotin-conjugated interferon- γ monoclonal antibody) (Mabtech) in PBS at a final concentration of 1microg/ml will be added, and the plate will be incubated for 2h at 37°C. The plate will then be washed four times with PBS containing 0.1% Tween-20. Avidin-bound biotinylated horseradish peroxidase H (Vectastain Elite ABC kit; Vector Laboratories, Inc., Burlingame, CA) will be added for 1h at 37°C. After four washings with PBS containing 0.1% Tween-20, stable diaminobenzene (Open Biosystems, Huntsville, AL) will be added to develop the reaction. The plates will be washed with distilled water three times and air-dried overnight.

The spots formed by interferon-gamma-secreting T-cells will be counted with an automated ELISPOT analyzer (AID ELISPOT Classic Reader; Autoimmun Diagnostika GmbH, Strassberg, Germany). The average spot-forming units (SFU) per antigen will be calculated. A response will be considered positive when the average SFU in wells with a given peptide was at least twice that of the average SFU in the no-peptide control wells.

Data analysis: Number of patients testing positive for each PSA peptide will be described. The statistical significance of the response will be assessed using paired t-test comparing SFU in peptide containing wells and those in no-peptide wells.

Study Population

Inclusion Criteria:

- Histological documented diagnosis of prostate cancer
- 18 years of age or older
- Signed informed consent form approved by the University of Arkansas for Medical Sciences (UAMS) IRB

Exclusion Criteria:

- Subjects must have no other current malignancies. Subjects with prior history at any time of any basal or squamous skin cancer are eligible, provided they are disease-free at the time of registration. Subjects with other malignancies are eligible if they have been continuously disease free for ≥ 5 years prior to the time of registration

Consent Process

Potential subjects with prostate cancer will be identified in the UAMS Medical Oncology or Urology clinic during routine clinic appointments. Upon identification, patients will be informed regarding the study by their physician along with the research staff. Patients will be allowed to review the IRB-approved informed consent form, and if they would like to participate in the study, they will sign the informed consent form.

During the consent process, the individual consenting patients will clearly be informed that their participation in this study is voluntary and that the decision whether or not to participate in the study will have no effect on future clinical care. The research subject will be encouraged to have family or friends participate in any or all of the process. The research subject will be provided sufficient time to ask questions, and will be questioned to ensure they understand the information. If they agree to proceed, the subject will sign the consent form. The consent process will be documented in the medical record. A copy of the informed consent document will be provided to the research subject, and additional copies will be sent to the medical records department. The original informed consent will be filed with the subject file in Cancer Clinical Trials Office (CCTO). The consent process will occur in a private exam room or in the private office of the research nurse.

Risks and Benefits

This is a minimal risk study (risk of phlebotomy; bruising, pain etc.) Potential benefits of this study may include the ability to contribute further research in this area. We anticipate that the data will help us better understand how to develop a prostate cancer vaccine.

Data Handling and Recordkeeping

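### ELISPOT positivity rests on a two-fold ratio alone, with no minimum excess over control, so at low background chance alone would inflate the per-peptide counts

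*Combined protocol and SAP*

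**What the plan says.** The rule is in Study Design and Procedures of the combined protocol and SAP. Positivity has a single condition: "the average SFU in wells with a given peptide was at least twice that of the average SFU in the no-peptide control wells". No second condition follows: no minimum difference, minimum spot count, criterion on replicate variability, ceiling on background or rule for a zero control mean.

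The assay conditions are in the same section: "Three hundred thousand PBMC per well in triplicate will be presented with 10microM each of the PSA peptides described above". The controls are described thus: "Phytohemagglutinin will be used as a positive control while media containing no peptide will serve as a negative control". The number of no-peptide wells is not given separately. On interleukin-2 the section says: "Human recombinant interleukin-2 (R&D Systems, Inc., Minneapolis, MN) (20U/ml) will be added to all wells". Neither an expected nor a historical background count appears anywhere.

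The Data analysis paragraph plans two results. The first uses the rule: "Number of patients testing positive for each PSA peptide will be described". The second does not: "The statistical significance of the response will be assessed using paired t-test comparing SFU in peptide containing wells and those in no-peptide wells".

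**The concern.** A ratio of two small counts is unstable. If the three control wells hold two spots in total, four spots over three peptide wells make the patient positive, a difference of two spots. When background is low this happens often with no peptide effect at all. Interleukin-2 in every well may raise background, but the documents do not say to what level, so the low range cannot be excluded.

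What is at stake is the reading of the counts. The introduction states the purpose: "In this protocol we focus on the immunogenicity of candidate peptides". It also values peptides that would serve all patients and not only those with certain tissue types. The number of positive patients per peptide is the planned result that speaks to that breadth. With 10 patients, one to three chance positives per peptide is a large share of any count and blurs the differences between peptides.

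Read literally, zero spots against zero spots also satisfies the rule. That is a wording error with little numerical effect except at very low background.

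**Working it through.** The plan states no false-positive rate, power or sample-size basis, so there is no figure of its own to reproduce.

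**Inputs from the protocol:** a two-fold rule on means; three wells per peptide; 10 patients.

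**Assumed:** background m SFU/well, varied from 0.5 to 10; Poisson spots; three control wells, shared by all peptides; no true response.

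**Formula.** Let X be the control total and Y the peptide total over three wells each, independent Poisson(3m). With equal numbers of wells the rule is Y ≥ 2X, so

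P(positive) = Σₓ P(X = x) · P(Y ≥ 2x).

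**Worked case, m = 1 (both totals Poisson with mean 3):**

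- x = 0: 0.0498 × 1.0000 = 0.0498
- x = 1: 0.1494 × 0.8009 = 0.1196
- x = 2: 0.2240 × 0.3528 = 0.0790
- x = 3: 0.2240 × 0.0839 = 0.0188
- x = 4: 0.1680 × 0.0119 = 0.0020
- x = 5: 0.1008 × 0.0011 = 0.0001

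The sum is 0.269. Expected positives among 10 patients are 10 × 0.269 = 2.7, and the binomial probability of 3 or more of 10 is 53%.

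| Background (SFU/well) | Chance-positive rate | Expected of 10 | P(3 or more of 10) |
|---|---|---|---|
| 1 | 26.9% | 2.7 | 53% |
| 2 | 15.6% | 1.6 | 20% |
| 3 | 9.8% | 1.0 | 6.6% |
| 5 | 4.2% | 0.4 | 0.7% |
| 10 | 0.6% | 0.06 | below 0.1% |

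**Zero against zero.** Excluding it moves the rate from 38.8% to 33.8% at m = 0.5 and from 26.9% to 26.7% at m = 1.

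**Sensitivity of the chance-positive rate to the assumptions:**

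| Setting | m = 1 | m = 3 | m = 5 | m = 10 |
|---|---|---|---|---|
| Two control wells | 31% | 14% | 7.2% | 1.6% |
| Three control wells | 27% | 9.8% | 4.2% | 0.6% |
| Six control wells | 20% | 4.9% | 1.4% | 0.1% |
| Three, with 30% extra well-to-well CV | 28% | 12.5% | 7.4% | 3.3% |

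**Effect of a floor.** A minimum excess of f SFU/well adds the condition Y − X ≥ 3f. The exact test is one-sided: given X + Y, Y is binomial with probability 0.5, and p ≤ 0.05 is required. Detection is the probability of a positive call for a true three-fold response.

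| Rule | Chance positive, m = 1 | Detection, m = 1 | Chance positive, m = 3 | Detection, m = 3 |
|---|---|---|---|---|
| Two-fold only | 26.9% | 78% | 9.8% | 88.4% |
| Plus floor 2 | 1.3% | 55% | 7.5% | 88.4% |
| Plus floor 3 | 0.04% | 23% | 2.2% | 88.1% |
| Two-fold plus exact test | 1.5% | 43% | 3.2% | 87.8% |

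At m = 10 a floor of 2 or 3 changes nothing: chance positives stay at 0.6% and detection at 98.1%. The two-fold rule with the exact test has a peak chance-positive rate of 3.3%, at m = 4.2.

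**Mixed backgrounds** (patients equally at 1, 2, 3, 5 and 10), chance positive and detection: two-fold only 11.4% and 88.5%; floor 2, 3.8% and 83.7%; floor 3, 1.4% and 75.5%; floor 2 plus exact test 2.1% and 79.4%.

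**The case against.** The strongest objection is that the harm depends on a number nobody has. Between 1 and 10 SFU/well the chance-positive rate falls from 27% to 0.6%, and with interleukin-2 in every well the background may not be low. The limit of about 3 is also soft, because it moves with the unstated number of control wells and with overdispersion. All of this stands, and it makes the finding conditional. It does not remove the finding: the plan does not exclude the low range, and a modest floor costs nothing where background is high.

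The consequence is also limited. The counts are descriptive, no selection rule uses them, and significance is left to a t-test that ignores the two-fold rule. This stands and keeps the point from being more serious. The t-test is a group-level comparison, however, and does not correct the counts.

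Finally, an early screen may reasonably favour sensitivity, and the remedy is imperfect. At background 1, a floor of 2 lowers detection from 78% to 55%. The exact test relies on Poisson wells: with 30% extra CV independent between wells, the two-fold rule plus the test gives 4.9% chance positives at background 3 and 5.9% at 5. If that variation is shared within a triplicate, the figures are about 8% and 11%. These are real costs and limits. They are the reason to set the floor from the laboratory's own data and to use the exact test as a sensitivity analysis, not as the main rule.

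**Conclusion.** The concern holds and should be fixed. The positivity rule is a ratio with no minimum excess, and nothing elsewhere in the plan adds one. If background is about 3 SFU/well or lower, an inert peptide is expected to show about 1 positive patient of 10 at a background of 3, rising to 2.7 at a background of 1. The effect is mild at 5 and small at 10 or above. These sizes rest on Poisson spots, three control wells and an assumed background; fewer control wells or extra well-to-well variation make them worse, and more control wells make them better. Confidence is medium because the background is unknown. The t-test on SFU and patient care are not affected.

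**What to change.** Before study counts are seen, amend the positivity rule and the Data analysis paragraph as follows.

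1. Keep the two-fold ratio, and require in addition that the peptide mean exceed the no-peptide mean by a stated minimum number of SFU/well. The minimum must be greater than zero, so that zero against zero is never positive, and the laboratory should set it from its own no-peptide wells under the same assay conditions.
2. State the expected background and the number of no-peptide wells.
3. Report, as a sensitivity analysis, the counts that also require a one-sided exact test (p ≤ 0.05) on the triplicate totals, because one floor may not suit patients with different backgrounds.
4. As a secondary clarification, state that a sample whose phytohemagglutinin wells fail is non-evaluable, and report positives over evaluable patients.

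The cost is a few sentences and a look at earlier no-peptide counts, if the laboratory has them; no new patients, blood or wells are needed. The downside is lost sensitivity to weak responses at very low background. A floor far above background must be avoided: at background 1, detection of a three-fold response falls to 23% with a floor of 3 and to 1% with a floor of 5. A floor too small for the background helps little: a floor of 2 at background 3 moves chance positives only from 9.8% to 7.5%.

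### Do five or six unadjusted paired t-tests against one shared control need a multiplicity correction?

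*Combined protocol and SAP*

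**What the plan says.** Inference is covered by one sentence in the Data analysis paragraph of Study Design and Procedures: the "statistical significance of the response will be assessed using paired t-test", with counts in peptide wells set against counts in no-peptide wells. The same paragraph first announces a descriptive result: "Number of patients testing positive for each PSA peptide will be described". A patient counts as positive for a peptide when the mean count is at least double that of the control wells.

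The plan does not say outright that each peptide is tested separately. It is the natural reading, because "The average spot-forming units (SFU) per antigen will be calculated" and positives are counted by peptide. The control is common to all peptides: "media containing no peptide will serve as a negative control".

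The number of tests is not settled. The text says "Five PSA peptides have been selected for" certain properties, but the list that follows has six entries and ends with "PSA 241-261 (Ac-SLYTKVVHYRKWIKDTIVANP-NH2". Ten patients are planned.

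The opening paragraph gives the aim as to "collect information in regards to the immunogenicity of PSA peptides in order to develop a novel therapeutic vaccine". No significance level, sidedness, multiplicity rule, power statement or description of the p-values as exploratory appears anywhere.

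**The concern.** Several candidates are screened side by side and each is given its own significance test. The chance that at least one inactive peptide passes is therefore well above the nominal level of a single test. All comparisons in a patient use the same control wells, so a chance-low control raises every difference together, and several peptides may look active at once. The protocol describes no replication cohort, and the results are meant to inform vaccine development and may be published. If a p-value below 0.05 decided which peptide went forward, an inactive one could be taken up by chance.

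**Working it through.** The plan states no error rate or power, so there is no figure of its own to reproduce.

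**Inputs from the plan:** 10 patients (9 degrees of freedom per paired t-test); k = 5 or 6 peptides; peptide wells in triplicate; one common no-peptide control.

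**Assumptions:** one test per peptide, two-sided 5%, control wells also in triplicate, no active peptide.

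**1. Independent tests.** P(at least one rejection) = 1 − 0.95^k.
- k = 5: 1 − 0.95^5 = 22.6%
- k = 6: 1 − 0.95^6 = 26.5%

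**2. Shared control.** Each difference is peptide minus the same control. Two differences then correlate at Var(control) / [Var(control) + Var(peptide)], which is 0.5 when the variances are equal. Positive correlation makes false rejections cluster, which lowers the chance of at least one. Simulated results:

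| Model | k = 5 | k = 6 |
|---|---|---|
| Normal, correlation 0.2 | 22.1% | 25.6% |
| Normal, correlation 0.5 | 19.0% | 21.5% |
| Normal, correlation 0.75 | 14.7% | 16.4% |
| Poisson triplicates, gamma patient backgrounds | 17.9% | 20.7% |
| Poisson triplicates, lognormal backgrounds (SD 0.8) | about 17.5% | about 20% |

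The 26% figure therefore belongs to independent tests, which the shared control rules out.

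**3. Direction.** A response means peptide above control, so a rejection in the other direction cannot mark a peptide as immunogenic. Counting upward rejections only:
- Independent: 1 − 0.975^5 = 11.9%; 1 − 0.975^6 = 14.1%
- Correlation 0.5: 9.6% (five), 10.8% (six)
- Poisson, gamma backgrounds: 9.0% and 10.4%
- Poisson, lognormal backgrounds: about 8.7% and 10%

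The comparable figure for a single test is 2.5%. If the analyst instead used one-sided 5% tests, the rates at correlation 0.5 would be 17.3% and 19.3%.

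**4. What the responder count adds.** In the lognormal-background simulation with six inactive peptides, an upward rejection together with at least 3 of 10 patients positive occurred for some peptide in 6.3% of trials at a background of 2 spots per well, 1.2% at 5 and 0% at 15. The cut of 3 in 10 is an assumption; the plan sets none.

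**5. What a correction would cost.** Holm's first threshold is 0.05/6 = 0.0083 (0.05/5 = 0.0100 for five). With all peptides inactive, the chance of any rejection falls to about 3-4%. The power figures below are for one active peptide and assume a background of 5 spots per well and 2- to 10-fold responses in responders:

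| Test | 60% responders | 80% responders |
|---|---|---|
| Planned raw counts, unadjusted | about 48% | about 76% |
| Raw counts at 0.0083 | 7% | 24% |
| Raw counts, max-T sign-flip | 13% | 36% |
| Log ratio, unadjusted | about 81% | about 98% |
| Log ratio at 0.0083 | 42% | 84% |

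On the planned scale, the correction loses 76 − 24 = 52 points of power at 80% responders and 48 − 7 = 41 points at 60%. The more favourable last row depends on a second change, to log ratios. Within that analysis the correction still costs 81 − 42 = 39 and 98 − 84 = 14 points.

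**The case for a change.** The strongest case for a change is that the error is real and cheap to acknowledge. With the shared control, the chance of an upward false lead somewhere in the panel is about four times that of a single test. In about 5% of simulated trials with six inactive peptides, two or more reached p < 0.05 together, which a reader could take for corroboration. The plan does not require the twofold rule to be met alongside the t-test, so the rule does not formally cap the error. Nor are the p-values labelled nominal. With a log-ratio analysis, Holm's correction would still give 84% power at 80% responders, more than the planned unadjusted test.

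The arithmetic stands, and so does the observation that the plan is silent on level and sidedness. The consequence is weaker than it looks. No passage lets a p-value choose a peptide. Solubility and the ability to mature Langerhans cells are named as further requirements and lie outside this protocol. The count of positive patients is reported beside the test, and in the simulations it usually failed to support a chance rejection, though less reliably at very low background. The log-ratio argument is really an argument for another test scale: it does not show that familywise control is needed, and at 60% responders the corrected log-ratio test (42%) is no better than the plan's own (about 48%).

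**Conclusion.** No change to the plan follows. With two-sided 5% tests and a shared control, a panel of inactive peptides gives some rejection in about 17-21% of trials, and a misleading upward one in about 9-11%. Those figures rest on assumed level, sidedness, per-peptide testing and triplicate controls, and they move with the ratio of control to peptide variability.

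In a 10-patient, minimal-risk study meant to gather information for later work, missing an active peptide may cost more than following one false lead. Familywise control is then a choice rather than a requirement, and on the planned scale its price is most of the power. The power figures depend on the assumed background and fold responses, but in both scenarios the loss is large.

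What remains is missing detail that a competent analyst supplies when reporting: the level and sidedness used, results for every peptide tested, and p-values read as nominal beside the responder counts. The mismatch between five and six peptides is clerical for this question; it moves the shared-control rates by about one to three percentage points and does not affect the conclusion.
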